## **2. Aims of the project**

The primary aim of the proposed randomized control trial is to investigate the effect of a kyphosis-specific exercise intervention on reducing the angle of kyphosis in Chinese older adults with thoracic hyperkyphosis. The secondary aim of this trial is to evaluate the effect of the kyphosis-specific exercise intervention on improving the self-image, pain, and physical performance in Chinese older adults with thoracic hyperkyphosis.

## **3. Study sites**

Participants will be recruited from the community centers in Wuhan, China.

## **4. Planned sample size**

It is planned to recruit 156 participants, and 20 participants for pilot.

## **5. Measurements**

The participants meeting the inclusion criteria will be arranged to finish spine measurements, physical performance tests, and questionnaires (Appendix 1).

### **6.1 Spine measurements (Primary outcome)**

The angle of kyphosis will be measured by manual inclinometer in the proposed study. There are two reasons we do not use X-ray, the gold standard. First, the study will be conducted in community centres without access to the X-ray facilities. Second, the participants will accomplish the angle of kyphosis measurement in two postures in three time points within 12 weeks. Manual measurements can protect the participants from exposing to unnecessary radiation.

Manual inclinometer is have previously demonstrated excellent levels of inter-rater ( $ICC=0.90$ ), and intra-rater reliability ( $ICC=0.92$ ) (Barrett, McCreesh, & Lewis, 2013), and satisfied concurrent validity ( $r=0.86$ ) (Barrett, Lenehan, O'Sullivan, Lewis, & McCreesh, 2018).

The angle of kyphosis will be measured in two conditions, once in participants standing relaxed, once in participants stand as straight as possible. The measurement procedure is as follow: 1) the researcher explaining measuring instructions; 2) participants exposing upper body in two standing posture; 3) identifying and marking the spinous processes of C7, T1, T2, T12, and L1 in two postures; 4) using manual inclinometers measure the angle in two postures. The measurements will also be performed three times in succession.

## **6.2 Physical performance assessments (Secondary outcomes)**

The physical performance assessments include two balance tests, One-leg Standing Test and Timed Up & Go Test; two cardiopulmonary function tests, the Thoracic Expansion test and the Six Minutes Walking Test; and a gait assessment, the Farsi Version of Functional Gait Assessment. All have been reported having satisfying validity and reliability (Kamrani, Seyed Hojjat Zamani Sani, Rezaie, & Aghdasi, 2010; Michikawa, Nishiwaki, Takebayashi, & Toyama, 2009; Wrisley, Marchetti, Kuharsky, & Whitney, 2004; Hu, Nan Liu, & Zhou, 2014).

## **6.3 Questionnaires (Secondary outcomes)**

Participants will also be given a set of questionnaires asking social-

demographic information and health-related information. Social-demographic information includes age, gender, marital status, and education level. The health-related information asks spine surgery history, illnesses, daily life posture, daily exercises level (via the International Physical Activity Questionnaire-Short Form) (Deng, Macfarlane, Thomas, Lao, Jiang, & Cheng, 2008). The self-image and pain will be measured via Scoliosis Patient Questionnaire - version 22 which has been found suiting for the evaluation of thoracic hyperkyphosis patients (Petcharaporn, Pawelek, Bastrom, Lonner, & Newton, 2007) and having a validated Chinese version (Cheung et al., 2007). The height and weight of participants will also be recorded in the questionnaire after measurement.

## **6. Estimated duration and commencement date**

Proposed starting date: 19/08/2019

Proposed study completion date: 01/03/2021

Expected final report date: 01/09/2021

## **7. Scientific/historical background**

Thoracic hyperkyphosis refers to an exaggerated curvature between the first thoracic vertebra body (T1) and the 12th thoracic vertebra body (T12) (Katzman, Wanek, Shepherd, & Sellmeyer, 2010) has a high prevalence among older adults. Studies reported that the prevalence of the thoracic hyperkyphosis in elderly ranged from 20% to 40% among community-dwelling subjects aged  $\geq 60$  years (Hinman, 2004; Kado, Huang, Karlamangla, Barrett-Connor, & Greendale, 2004; Takahashi et al., 2005). The cross-sectional study conducted by the Principal Investigator found thoracic hyperkyphosis have a high prevalence (72%) in Chinese community-dwelling older adults.

Thoracic kyphosis has been found having negative effects on health. An increased angle of thoracic kyphosis was related to decreased self-image diminished physical function, impairment of respiratory function, increased

chronic upper back pain, decreased balance, decreased quality of life, and decreased gait performance (Petcharaporn et al., 2007; Huang, Barrett, Greendale, & Kado, 2006; Kado, 2017; Kado, Huang, Barrett, & Greendale, 2005; Sangtarash, Manshadi, & Sadeghi, 2015).

Treatment options of thoracic hyperkyphosis included surgery (Katzman, Wanek, Shepherd, & Sellmeyer, 2010), peptides injection (Liu, Wu, & Li, 2004), menopausal hormone therapy (Woods et al., 2018), bracing (Zaina et al., 2009), traditional Chinese medicine therapies (Shen, 2011). Exercise, a noninvasive and less pain treatment method, has also been conducted for relieving thoracic hyperkyphosis abnormality (Seidi, Rajabi, Ebrahimi, Alizadeh, & Minoonejad, 2014; Senthil, Sudhakar, Radhakrishnan, & Jeyakumar, 2017).

The previous studies reported that different types of exercise such as strength training, pilates, yoga, and corrective exercise were effective in reducing the thoracic hyperkyphosis (Greendale, Huang, Karlamangla, Seeger, & Crawford, 2009; Katzman et al., 2010). Investigator conducted a systematic review in order to explore the most effective exercise intervention for thoracic hyperkyphosis correction.

According to the systematic review, the most popular kyphosis-specific exercise protocol was designed by Katzman and team. There were two versions of the protocol, one published in 2007 (Katzman, Sellmeyer, Stewart, Wanek, & Hamel, 2007), another published in 2016 (Katzman et al., 2016). One third of 12 selected studies used this protocol, and two of them reported the largest decrease of the angle of kyphosis.

Both of the two studies with largest angle change reported more than 5° angle decrease. One was pre-post cohort study conducted by Katzman and team (2007) reported from baseline to post-intervention, the angle of kyphosis decreased  $6^\circ \pm 3^\circ$  ( $p < 0.001$ ) in relaxed standing posture, and  $5^\circ \pm 3^\circ$  ( $p < 0.001$ ) decrease in best standing posture. Another one was RCT conducted by Bahrekazemi and colleagues (2017) used the protocol published in 2016. They found the intervention group having a  $6.5^\circ$  mean angle reduction within group ( $p < 0.05$ ), and a  $6.8^\circ$  mean angle

reduction between groups ( $p<0.05$ ).

Another two studies also found a statistically significant change of the kyphotic angle. One RCT reported that within the intervention group, the angle of kyphosis decreased by  $3.3^\circ$  (95% CI  $-4.9, -1.7$ ), compared to a decrease of  $0.3^\circ$  (95% CI  $-1.9, 1.2$ ) among controls (Katzman, Vittinghoff, et al., 2017). Another reported participants in the intervention group had a  $3.8^\circ$  (95% CI:  $-5.3$  to  $-2.3$ ) decrease in the angle of kyphosis while the control group had an insignificant change ( $1^\circ$ , 95% CI:  $-0.5$  to  $2.4$ ), between-group difference was  $4.8^\circ$  ( $p< 0.001$ ) (Katzman, Parimi, et al., 2017).

However, the 12 systematic review selected studies either excluded older adults have and exercise habit or lack of information about participants' daily activity level. Thus there is a lack of information about the effectiveness of kyphosis-specific exercise intervention on reducing the angle of kyphosis in older adults having exercise habit. The cross-sectional study conducted by the Principal Investigator found that older adults in Wuhan, China were active in daily life that more than 92.5% of the participants with thoracic hyperkyphosis reported moderate or high exercise intensity.

Currently, multimedia education has been successfully employed in healthcare fields (Batuyong, Birks, & Beischer, 2012). For example, exercise video has been used to help patients mastering the pelvic floor muscle exercise (Crowe, Harbison, Wootten, Pillay, & Morrison, 2018), preventing shoulder problems (Park, & Song, 2017), and enhance exercise adherence of patients with osteoarthritis of the knee (Tohyama, Chiba, Tadano, Ikoma, & Yasuda, 2010).

Video is a promising method for giving exercise intervention to elderly. Because the video can provide accurate visual guidance on how to perform the exercises and, in addition, music and verbal instruction can be motivational during the exercises (Vestergaard, Kronborg, & Puggaard, 2013). Using video as intervention can also overcome the limitations on finance and transportation when the elderly wants professional exercise guidance.

All the kyphosis-specific exercise interventions in reviewed studies by the

Principal investigator were delivered by professional trainer or physical therapist in the form of face-to-face exercise class. No evidence shows whether the kyphosis-specific exercise intervention be given in the form of video also have effects on reducing the angle of kyphosis or enhancing the overall physical performance in older adults with thoracic hyperkyphosis.

So, it is valuable to conduct the proposed study providing kyphosis-specific exercise in the form of video and face to face exercise class as intervention to Chinese older adults with thoracic hyperkyphosis. The proposed study can test the effects of such kyphosis-specific exercise intervention on the angle of kyphosis, physical performance, pain, and self-image among Chinese older adults with thoracic hyperkyphosis.

## **8. Research question and hypotheses**

### **9.1 research questions**

- 1) what are the effects of kyphosis-specific exercise intervention (video and exercise class) on the angle of kyphosis in Chinese elderly with thoracic hyperkyphosis, as compared with control?
- 2) what are the effects of kyphosis-specific exercise intervention (video and exercise class) on pain, self-image, and physical performance, including gait performance, balance, and cardiopulmonary functions in Chinese elderly with thoracic hyperkyphosis?

### **9.2 Hypothesis**

- 1) older adults receive kyphosis-specific exercise intervention (video and exercise class) have reduced the angle of kyphosis;
- 2) older adults receive kyphosis-specific exercise intervention (video and exercise class) have decreased pain, better self-image, and improved the overall physical performance.

## **9. Study design**

### **10.1 Study type**

The proposed study is a single blinded randomized control trial. The participants and kyphosis-specific exercise intervention instructor are not able to be blinded, while the people conducted assessments will be blinded for group allocation.

### **10.2 Method of selection of subjects**

The target population will be elderly living in Wuhan, Mainland China. The older adults participated in the previous cross-sectional study conducted by the principle investigator will be first invited.

Inclusion criteria for subjects to be screened are:

- 1) Chinese;
- 2) Aged 60 years and above;
- 3) No cognitive impairment or communication problems;
- 4) The angle of thoracic kyphosis  $> 40^\circ$  measured by Manual Inclinometer;
- 5) Able to decrease the angle of kyphosis of  $5^\circ$  while standing.

Exclusion criteria for subjects to be screened include:

- 1) Having central or peripheral neuropathy (this may affect balance);
- 2) Taking drugs that affect the nervous system or affect balance and strength;
- 3) Having untreated severe heart and lung disease (this may affect cardiopulmonary function);
- 4) Having a history of spinal fracture (this may increase the risk of injury);
- 5) Having surgery in spinal, shoulder, and pelvis in the past year or having plan to do so in the coming six month (this may increase the risk of injury);
- 6) Having scoliosis  $\geq 10^\circ$ ;
- 7) Having done any specific therapeutic exercise for posture in the past year or having plan to do so in the coming six month (may affect the study result).

#### **10.4 Number of subjects to be recruited**

According to the systematic review, the effect size of four studies used Katzman's kyphosis-specific exercise protocol ranged from 0.44 to 2.45 (Bahrekazemi, et al., 2017; Katzman, Vittinghoff, et al., 2017; Katzman, Parimi, et al., 2017; Katzman, Sellmeyer, Stewart, Wanek, & Hamel, 2007). We expect the proposed RCT can attain similar effect size, hence for a more conservative estimate, effect size 0.44 (which was equivalent to intervention group had the angle of kyphosis 3.0°, 95% CI 0.56°-3° less than the controls) was taken into sample size calculation. Assuming the level of significance at 0.05 and power as 0.8, the calculated sample size will be in each group. The proposed study will recruit at least 78 participants in each group taking a drop-out rate of 20%. In the pilot study, 20 eligible participants will be recruited.

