#### **10.5 Procedures**

The participants are to be selected from the communities located in different regions in Wuhan by convenient sampling. The participants joined the cross-sectional study conducted by principal investigator in 2018 will be first invited. The staff working in community centers will also send notice to the residents' online chat room. Every potential participant will have a trained research assistant responsible for explaining the RCT details with the information sheet (Appendix 3) and re-assuring the respondents that data collected in the study will be kept strictly confidential, and then seeking permission for conducting the screening. The potential participants will be screened according to inclusion and exclusion

[figure not shown]
criteria (Appendix 4). The eligible participants will sign the written consent (Appendix 5) and accomplish the baseline questionnaire and assessments (T0). After that the participant will be randomly divided into intervention group or control group.

Block randomization method will be used (Kang, Ragan, & Park, 2008). The investigator will randomly select block sizes such as two, four, or six, to make randomization sequences for 156 participants. Then randomization sequences will be printed and placed in a sequentially numbered opaque sealed envelope. After older adult sign consent and finishing the baseline questionnaire and assessments, the researcher will open the envelop according to the numbered sequence for the grouping allocation.

The intervention group will receive kyphosis-specific exercise class, kyphosis-specific exercise video and a log book (sample page is shown in Appendix 6). Before every exercise class, the researcher will send them time and location as reminders. Class attendance is recorded every time. The participants are asked to record the time of home kyphosis-specific exercise practice and other daily exercises. They can also write down questions about kyphosis-specific exercise in the log book. The investigator will check the log book and respond to the questions once a week. The Control group will receive a booklet introducing general health education material, and a log book recording the time of daily exercises (sample page is shown in Appendix 7).

After the end of 6 weeks intervention, all participants will be invited to finish the postintervention assessment (T1). The flowchart of the proposed RCT is presented in Figure 1.

**Figure 1** The flowchart of proposed RCT

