## **10. Methods of statistical analysis**

The data will be analyzed according to intention to treat. Descriptive statistics will be used to explore the characteristics of the elderly.

The primary outcome is the change in the angle of kyphosis. The secondary outcomes are the score change of pain and self-image, the change in score of the Farsi version of Functional Gait Assessment, change in time of the Timed Up and Go Test and the One Leg Standing Test, change in walking distance of the Six Minutes Walking Test, and change in length of the Chest Expansion test.

T-test and Chi-square test will be used to determine any baseline differences among two intervention groups and one control group in terms of baseline socio-demographics, regular exercise type and intensity, illness condition, and the angle of kyphosis.

Linear mixed effect model will be conducted to explore the between-group and within-group differences in the outcomes across the time, while controlling socio-demographics, illness condition, BMI, type and intensity of regular exercise. SPSS version 23.0 was used to analyze data collected, the significance level will be 0.05.

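### Section 10.4: 80% power with 78 per group rests on an input the plan does not declare; a two-sided test without baseline adjustment has about 68%

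*Combined protocol and SAP*

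**What the plan says.** Section 4 sets the total: "It is planned to recruit 156 participants". Section 10.4 takes an effect size of 0.44, described as conservative and equated with a 3.0° difference between groups. It continues "Assuming the level of significance at 0.05 and power as 0.8" and ends "The proposed study will recruit at least 78 participants in each group taking a drop-out rate of 20" (per cent). The number per group before drop-out does not appear in the text as read. It may have been lost from the file, and its absence is not treated as an error here.

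The section on methods of statistical analysis states: "The primary outcome is the change in the angle of kyphosis". It plans a linear mixed model for differences between and within groups over time, and gives the adjustment as "while controlling socio-demographics, illness condition, BMI, type and intensity of regular exercise". On the test it says only "the significance level will be 0.05". Baseline angle is not in the covariate list, and the section does not say how the baseline measurement (T0) enters the model.

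No section states whether the test is one- or two-sided, which formula produced 78, or any assumed correlation between baseline and follow-up.

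**The concern.** Effect size, significance level, power and drop-out rate are all given, so a reader can recompute the sample size. The usual two-sided calculation gives a clearly larger number than 78. Even with every one of the 78 retained, power falls just short of 80%.

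The 80% matters most if the primary result is not significant. A reader would then take the trial as having had a four-in-five chance of detecting 3.0°, and would weigh the result against the exercise programme accordingly. If the true figure is nearer two in three, that inference is too strong. Leaving sidedness undeclared also leaves the primary decision rule open until the data have been seen.

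**Working it through.** **Inputs.** Effect size d = 0.44, difference 3.0°, significance 0.05, power 0.80, drop-out 20% and 78 per group come from section 10.4. The total of 156 = 2 × 78 is in section 4. The implied SD is 3.0/0.44 = 6.8°. Completers are 78 × 0.8 = 62.4, taken as 62. Assumptions: equal variances, no gain from the listed covariates (no figures are given for them), and, except in step 5, the two visits T0 and T1 of section 10.5. All results use the noncentral t distribution.

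**1. Reproducing 78.** Two routes give it.
- Two-sided, baseline-adjusted, correlation r = 0.5: d becomes 0.44/√(1 − 0.25) = 0.508; n = 61.79, so 62; 62/0.8 = 77.5, so 78.
- One-sided at 0.05: n = 64.56, so 65; 65 × 1.2 = 78. The usual inflation, 65/0.8 = 81.25, gives 82. Power at 62 completers is 0.786.

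The first route depends on r being close to 0.5: r = 0.4 gives 70 completers (88 recruited) and r = 0.6 gives 53 (67).

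**2. Two-sided, no baseline adjustment.** n = 82.05, so 83 completers; 83/0.8 = 103.75, so 104 recruited per group. Power at 62 completers is 0.681; at 78 it is 0.780. With 62 per group, 80% power is reached at d = 0.507, and 0.507 × 6.8 is about 3.5°.

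**3. How the treatment of T0 changes power.** Let σ be the SD of the angle at one visit. A comparison of change has SD σ√(2(1 − r)); a baseline-adjusted comparison has SD σ√(1 − r²). The standardised effects are:
- 0.44 on the follow-up SD: 0.44/√(2(1 − r)) for change, 0.44/√(1 − r²) adjusted.
- 0.44 on the change SD: 0.44 for change, 0.44 × √(2/(1 + r)) adjusted.

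Two-sided power with 62 completers per group:

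| r (assumed) | Change, follow-up SD | Adjusted, follow-up SD | Change, change SD | Adjusted, change SD |
|---|---|---|---|---|
| 0.3 | 0.54 | 0.72 | 0.68 | 0.85 |
| 0.5 | 0.68 | 0.80 | 0.68 | 0.80 |
| 0.6 | 0.78 | 0.86 | 0.68 | 0.78 |
| 0.8 | 0.97 | 0.98 | 0.68 | 0.73 |

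A mixed model that treats T0 as a repeated response with free group means tests change. Keeping the T0 values of the 16 drop-outs per group gives a per-arm variance of (1 − r²)/62 + (1 − r)²/78 in units of σ². At r = 0.5 this raises power only from 0.68 to 0.70.

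**4. Which scale 0.44 is on.** Section 7 reports, for one of the cited trials, a fall of 3.3° with exercise and 0.3° in controls: 3.3 − 0.3 = 3.0°. The 3.0° is thus a difference in change. If 0.44 is scaled on the SD of change, a completer comparison of change stays at 0.68 whatever r is. Section 10.4 does not name the SD.

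**5. Three visits.** Section 6.1 says the angle is measured at three time points within 12 weeks; section 10.5 describes T0 and T1 only. Suppose there are two follow-ups, all correlations are 0.5, 0.44 is on the single-visit SD, and the contrast averages both follow-ups. The change variance is then 1.5 − 1.5r = 0.75, and power at 62 per group is 0.80 for change and 0.93 with baseline adjustment. A contrast at a single visit stays near the values in step 3.

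**The case against.** The strongest reply is that 78 is not a mistake. A correlation of 0.5 with baseline adjustment gives 62 evaluable and 78 recruited exactly, and the planned analysis is a covariate-adjusted mixed model, not a two-sample comparison of completers. The missing pre-drop-out number might also show which route was used. Much of this stands. The arithmetic behind 78 may be sound, and the 68% is a benchmark that depends on there being no gain from adjustment.

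It does not rescue the 80% as written. A mixed model does not by itself deliver the adjusted power. With T0 as a covariate, or with group means constrained equal at T0, it does; with free group means at T0 it compares change. The plan makes change the outcome and does not list baseline angle as a covariate. Recovering the missing number would point to a route, but would still not declare a correlation or a sidedness.

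A reader might argue that the directional hypotheses in section 9.2 imply a one-sided test. Directional wording does not declare one, and that route reaches 78 only by multiplying by 1.2.

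The visit-count objection also stands in part: the contrast between 0.68 and 0.80 holds for two visits, and an averaged contrast over two follow-ups could do better.

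**Conclusion.** The point holds as an unsupported power statement. On the declared inputs, with a two-sided test and no gain from baseline adjustment, 78 per group gives about 68% power after drop-out, about 12 percentage points below the stated 80%. With T0 and T1 only and r = 0.5, power is about 0.68 to 0.70 for a comparison of change and about 0.80 with baseline adjustment, and the plan does not commit to the latter.

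A reader might infer that the trial is underpowered, or that its authors miscalculated. The documents do not support either. An undeclared correlation near 0.5 reproduces 78, and a high correlation with 0.44 on the follow-up SD would put power well above 80%. The true correlation, the SD behind 0.44 and the number of visits in the primary contrast are all unknown from the text.

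**What to change.** Keep 156 participants and change the wording in two sections.

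- In section 10.4 and in the statistical analysis section, declare the primary test two-sided at 0.05.
- Make the primary analysis a mixed model with baseline angle as a covariate, or with group means constrained equal at T0, and name the primary visit. Reconcile the visit counts in sections 6.1 and 10.5.
- Restate the power for 62 completers per group: about 68% for 0.44 (3.0°) without baseline adjustment, with 80% reached at about 0.51 (3.5°); and about 80% for 0.44 with baseline adjustment under a stated assumed correlation of 0.5. Name the SD on which 0.44 is scaled and show the range over r. Show the drop-out step as 62/0.8 = 77.5, so 78.
- Drop the one-sided reading. If a one-sided test was truly intended, declare it in both sections and state about 79% power at 62 completers, not 80%.

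No extra participants or measurements are needed, since baseline angle is already collected. The downside is that the stated power becomes less favourable or rests openly on an assumed correlation, for which the 20-person pilot could give only a rough value.
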